2.4.2 Plasma markers of hemostatic activation, fibrinolysis, and angiogenesis

Trousseau first published the link between malignancy and thrombosis in 1865 (62). Since then, various physicians and scientists have studied this association in terms of thrombotic mechanisms, determinants of cancer prognosis, and treatment outcomes. Data from the MEGA study, a large population-based, case-control study, revealed that cancer increases the risk of venous thromboembolism 7-fold overall, with a higher risk near the time of diagnosis and with advanced rather than localized disease (63). The presence of a malignancy also increases the risk for recurrent venous thromboembolism (64, 65). In addition, both the Levitan study (64) and data from the Danish registries (66) found that thrombosis in the cancer patient predicts for worse prognosis and a shorter survival.

Even in the absence of clinical thromboembolic disease, abnormalities in coagulation tests in patients with malignancy are common. Elevation of coagulation factor levels, fibrin degradation products, and platelet counts are common (67). Other more specific parameters demonstrative of activation of hemostasis, including thrombin-antithrombin (TAT) complexes, fibrinopeptide A, D-dimers and prothrombin fragment F1+2, are also elevated. The hemostatic activation observed in many cancer patients may be the result of direct activation by the malignant cell or an indirect effect mediated through activated endothelium or monocytes (68, 69).

The link between early activation of hemostasis and cancer prognosis has also been demonstrated in clinical studies. D-dimers are a marker of fibrin formation and degradation by both thrombin and plasmin. The levels of D-dimers are elevated in a variety of clinical situations associated with increased thrombin generation such as disseminated intravascular coagulation and thromboembolic events. Clinical studies have shown that D-dimer levels are significantly elevated in many patients with both disseminated and limited malignancies without evidence of clinical thromboembolism (67). Quantitative measurements of D-dimers, using sensitive immunoassays, have been reported to have prognostic significance. The plasma level of D-dimers predicts survival in patients with both limited and disseminated lung cancer (70-72). Similarly, in women with breast cancer, levels of D-dimers have correlated with malignant versus benign breast lesions (73), the presence of lymph node metastases on surgical pathology (73), and with volume of disease, time to progression, and overall survival in metastatic disease (74). Quantitative D-dimer levels also correlate with levels of IL-6 and VEGF (74). In patients with colorectal cancer, pre-operative levels of D-dimer have been correlated with stage of disease, tumor size and or depth of invasion, lymph node metastases, and distant metastases (75). Levels of D-dimers have also correlated with FIGO stage in women with ovarian cancer (76). Pre-operative levels of plasma TAT complexes, an assay more reflective of immediate thrombin generation, have been correlated with risk of venous thrombosis in patients with cancer undergoing surgery (77). Plasma TAT levels have also been shown to correlate with response to therapy and prognosis in patients treated for lung cancer (78). In addition, there is evidence that inhibitors of coagulation may decrease tumor growth, limit metastases, and improve survival in cancer models (79-82).

Like many other cancers (as discussed above), prostate cancer is linked to thrombosis. In a review of patients with thrombosis with or without cancer using Medicare claims data, prostate cancer was the third most common type of malignancy to be associated with a thrombosis (64). Activation of both the coagulation and fibrinolytic systems has been demonstrated in prostate cancer (83). Clinically, men with carcinoma of the prostate are at increased risk of thromboembolic disease, but may also have increased risk of bleeding (84). The interaction of tumor cells with the coagulation and fibrinolytic systems is likely be important in tumor growth and spread. Markers of activation of coagulation, including D-dimers, TAT, and prothrombin fragment F1+2, are elevated in men with advanced prostate cancer compared to age-matched controls (85). TF expression (using immunohistochemistry) has also been correlated with angiogenesis and PSA level (86). In metastatic disease, immunohistochemical assessment of biopsy specimens for TF correlated with prognosis with androgen deprivation therapy (87). Preoperative levels of IL-6 and its receptor are associated with recurrence and progression in localized prostate cancer (88, 89). Increased VEGF expression correlates with Gleason score and pathologic stage in localized prostate cancer (90). However, in prostate cancer as in other cancers, it is unclear if expression of angiogenic markers in tumor tissue or neighboring normal tissue or stroma is more important prognostically (91-93).

[figure not shown]

2.4.3 Circulating tumor cells (CTCs)

Assays to detect CTCs in the peripheral blood of cancer patients have been used clinically to provide prognostic information and to test for minimal residual disease. Typical methods to detect these CTCs are either antibody-based (immunocytochemistry or flow cytometry) or RT-PCR; each has its specific advantages and limitations. For example, RT-PCR can be very sensitive and highly specific when the expression of the target mRNA is limited to malignant tumor cells. Flow cytometry, on the other hand, has been used to detect and authenticate cells as CTCs, but it does not allow visual confirmation of cell morphology or discrimination of changes at the subcellular level (97). The challenges in CTC detection relate to the need for high sensitivity combined with high specificity. Important progress in this field has recently arisen with the development of a semi automated enrichment system, the CellSearch (Veridex LLC, Warren, NJ) that uses an antibody-based immunomagnetic-capture and automated staining methodology (98). The immunomagnetic capture is achieved with the use of a ferrofluid-coated antibody specific for the epithelial cell adhesion molecule EpCAM (99), a 40 KD, transmembrane glycoprotein that consists of two epidermal growth factor-like extracellular domains. EpCAM, encoded by the *GA733-2* gene located on the long arm of chromosome 4 (100), has been described under various names, mostly associated with monoclonal antibodies specific for cell surface antigen (MH99, AUA1, MOC31, 323/A3, KS1/4, GA733, and HEA125 (used in this assay). Litvinov *et al.* first suggested the name EpCAM, which more precisely reflects the molecule's function and tissue specificity. EpCAM is detected at the basolateral membrane of the majority of epithelial tissues, and is overexpressed by the majority of human epithelial carcinomas, including colorectal, breast, prostate, and head and neck carcinomas (101). Thus, use of antibodies to EpCAM allows for circulating epithelial-derived tumor cells to be isolated and concentrated from peripheral blood so they can be further inspected by microscopy. However, as EpCAM, can also be expressed in leucocytes, the specificity of this antibody-based assay to detect CTCs is lowered to 80%. To increase the specificity of detection for epithelial tumor-derived cells, CellSearch technology uses three additional immunostains: an antibody against CD45 conjugated with allophycocyanin to identify white blood cells (WBC), the nuclear dye [4,6-diamidino-2-phenylindole (DAPI)] to fluorescently label the cells' nuclei, and two phycoerythrin-conjugated anti-cytokeratin antibodies recognizing cytokeratins (predominantly cytokeratins 8, 18, and 19) to more specifically identify epithelial cells as such. Stained cells are analyzed on a fluorescence microscope using the Cell Track Analyzer II. Automatically selected images are then reviewed by the operator for the identification and counting of CTCs. The criteria for an object to be defined as a CTC include: round-to oval morphology, a visible nucleus (DAPI staining), positive staining for cytokeratins, and being negative for CD45. In addition, the consensus pathognomonic features of epithelial tumor cells, such as a clearly enlarged nucleus, high nucleus/cytoplasmic ratio and/or clusters of two or more immunopositive cells are also part of the CTC definition criteria, further attesting to the epithelial-tumor specificity developed in the CellSearch method (for review see (102)). The accuracy, sensitivity and linearity of CTC detection by this method has been previously established (98).

Clinical studies of CTCs in humans with cancer: Using this system, Cristofanilli et al. show in a prospective study, that CTC detection provides significant prognostic information for patients with metastatic breast cancer (103). In this pivotal study, the detection of >5 CTCs per 7.5 mL of blood at the start of chemotherapy and after each cycle of therapy was associated with shorter progression-free and overall survival for patients with metastatic breast cancer. Another related study in metastatic breast cancer revealed that CTC counts are more predictive of outcomes than the standard clinical parameters (104). The CellSearch system and reagents have now been Food and Drug Administration–cleared for routine clinical use in metastatic breast, colorectal, and prostate cancer. Recent studies using this technology in prostate cancer also show that a count of >5 CTCs per 7.5 mL of blood is associated with poor overall survival, in this case in patients with metastatic PC (105, 106). Furthermore, in a subset of CRPC patients, the presence of CTCs was shown to be the most significant parameter predictive of survival in both univariate and multivariate analyses (105). These single institution findings have been confirmed with a multi-centered study (Moreno et al., American Society of Clinical Oncology 2007 Annual Meeting), leading to an application for FDA approval in prostate cancer. Finally, it has been demonstrated that CTC's isolated using this technology can be analyzed with immunohistochemistry, immunofluorescence, and FISH analysis, which has confirmed the neoplastic nature of these cells and demonstrated amplification of the androgen receptor (107). For these reasons, we believe this technology is the most advanced, sensitive, and appropriate for our CTC study. We will perform cell counting on 7.5 mL samples at baseline, 1 month (pre-J591 for that arm), 2 months, and at 6 months. We will analyze baseline levels (< 5 CTCs/7.5 mL blood vs ≥ 5) as well as changes with treatment for associations with PSA response and time to development of radiographically evident metastatic disease.

WCMC studies using CTCs in prostate cancer: We have been using the CellSearch system to count CTCs. However, using this methodology the enumerated CTCs cannot be retrieved for any further molecular analysis. Thus, we have collected an additional sample of blood which is subjected to automated immunomagnetic selection using the CellSearch profile kit allowing us to selectively collect the EpCAM-positive cells without any additional staining. Following isolation, isolated tumor cells may be assessed using a variety of methods. Since PSMA expression is universal, there has not been any selection of patients treated on any of our clinical trials utilizing J591. We will explore the utility of assessment of PSMA expression by immunohistochemistry (scored in quantitative fashion) of pre-treatment CTCs with relationship to response to Lu-J591.

PSMA staining in CTCs isolated from the blood of a CRPC patient. The EpCAM-enriched cells were isolated from the blood of CRPC patients and were further immunostained for PSMA (J591) and DAPI. **Left Panel:** Phase image of the ferrobead captured cells, showing the ferrobead location and the overall cell integrity. **Middle Panel:** PSMA immunostaining shows a distinct cell-membrane localization. **Right Panel:** Merged image of PSMA and DAPI staining. The diameter of the depicted cells is approximately 15 um.

2.4.4 Patient Reported Outcomes

Quality of life has not been well-described in men with non-radiographically evident CRPC. In addition, while the appearance of radiographically-evident metastatic disease is generally agreed to be a negative prognostic event, studies assessing the initial appearance of metastases have only sub-optimally examined patient symptoms.

The Functional Assessment of Cancer Therapy – Prostate (FACT-P) questionnaire is a validated tool to assess both global and prostate cancer specific symptoms and quality of life. The FACT-P (version 4) questionnaire will be completed by subjects at baseline and at each radiographic assessment timepoint (prior to results).

3. PATIENT SELECTION

3.1 Inclusion Criteria

3.1.1 Patients must have histologically or cytologically confirmed adenocarcinoma of the prostate.

3.1.2 Biochemical progression (rising PSA) after medical or surgical castration

- Subjects who have received antiandrogens (such as bicalutamide) and have experienced PSA decline must have biochemically (PSA) progressed following discontinuation of anti-androgen therapy.
- **PSA:** An increase in PSA determined by two separate measurements taken at least one week apart and confirmed by a third, and if necessary, a fourth measurement. If the third measurement is not greater than the second measurement, then a fourth measurement must be taken; the fourth measurement must be greater than the second measurement for the patient to be eligible for enrollment in the study. Furthermore, the confirmatory PSA measurement (i.e., the third or, if applicable, fourth PSA measurement) must be ≥ 1 ng/mL with prior prostatectomy or ≥ 2 ng/mL without prostatectomy and $\geq 25\%$ above the previous nadir.

3.1.3 High risk of systemic progression defined as:

- Rising PSA as defined above and either:
 - Absolute PSA > 20 ng/mL
AND/OR
 - PSA DT < 8 months

PSA doubling time (PSA-DT) will be calculated using a linear regression model. In the model, the logarithm of PSA will be modeled as a linear function of time. The PSA-DT will be calculated as the product of $\log 2$ multiplied by the reciprocal of the slope of the regression equation, for which the logarithm is the natural log function. For standardization purposes across sites, a web-based PSA doubling time calculator developed by Memorial Sloan Kettering, is available at <http://www.mskcc.org/mskcc/html/10088.cfm>

The minimum PSA value for eligibility will be greater than or equal to 1 with prior prostatectomy or at least 2 ng/mL without prostatectomy. All PSA values of at least 0.1 ng/mL over the past 6 months must go into the equation. A minimum of 3 PSA values with a minimum of 2 weeks between assessments is required (the screening PSA may be used for the 3rd value if necessary).

- 3.1.4 No evidence of local recurrence or distant metastases within 1 month of enrollment (or following enrollment as part of screening) including:
 - Radionuclide bone scan without evidence of metastatic disease
 - In the event of an equivocal bone scan, confirmation is needed with Xray, CT scan, or MRI
 - CT or MRI of abdomen/pelvis without evidence of metastatic disease or recurrent disease in the prostate or prostate bed
 - If no prior prostatectomy or radiation to the prostate, multiparametric MRI (mpMRI) of the prostate must have been performed and scored with PIRADS v2. The PIRADS score must be <3. (Appendix H: Summary of PIRADS V2 Scoring). mpMRI must be performed within 30 days prior to randomization.
 - Chest Xray or CT of chest without evidence of metastatic disease
 - Digital rectal exam (DRE) without clinical suspicion of recurrent/persistent prostate cancer
- 3.1.5 Age \geq 18 years.
- 3.1.6 Serum testosterone \leq 50 ng/ml
- 3.1.7 The effects of J591 on the developing human fetus at the recommended therapeutic dose are unknown. For this reason, patients capable of fathering children must agree to use an effective method of contraception for the duration of the trial.
- 3.1.8 Subjects on bisphosphonate therapy or denosumab must be on a stable dose and must have started therapy \geq 4 weeks prior to protocol therapy. Initiation of bisphosphonate therapy or denosumab is not allowed during the treatment phase.
- 3.1.9 Ability to understand and the willingness to sign a written informed consent document.

3.2 **Exclusion Criteria**

- 3.2.1 Use of red blood cell or platelet transfusions within 4 weeks of treatment
- 3.2.2 Use of hematopoietic growth factors within 4 weeks of treatment
- 3.2.3 Prior cytotoxic chemotherapy and/or radiation therapy within 4 weeks of treatment
- 3.2.4 Prior radiation therapy encompassing >25% of skeleton (see Appendix C)
- 3.2.5 Prior treatment with ⁸⁹Strontium or ¹⁵³Samarium containing compounds (e.g. Metastron®, Quadramet®)
- 3.2.6 Platelet count <150,000/mm³ or known primary qualitative platelet disorder
- 3.2.7 Absolute neutrophil count (ANC) <2,000/mm³
- 3.2.8 Hematocrit <30 percent and Hemoglobin < 10 g/dL
- 3.2.9 Abnormal coagulation profile (PT or INR, PTT > 1.3x ULN) unless on therapeutic anticoagulation – see concomitant meds section
- 3.2.10 Serum creatinine >2.5 mg/dL
- 3.2.11 AST (SGOT) >2x ULN
- 3.2.12 Bilirubin (total) >1.5x ULN; subjects with Gilbert's syndrome will be allowed if direct bilirubin is within institutional normal limits
- 3.2.13 Active serious infection
- 3.2.14 Active angina pectoris or NY Heart Association Class III-IV
- 3.2.15 ECOG Performance Status > 2
- 3.2.16 Life expectancy <12 months
- 3.2.17 History of deep vein thrombosis and/or pulmonary embolus within 1 month of study entry
- 3.2.18 Other serious illness(es) involving the cardiac, respiratory, CNS, renal, hepatic or hematological organ systems which might preclude completion of this study or interfere with determination of causality of any adverse effects experienced in this study
- 3.2.19 Prior investigational therapy (medications or devices) within 4 weeks of treatment. Furthermore, other investigational therapy is not permitted during the treatment phase.

- 3.2.20 Prior use of ketoconazole for the purposes of prostate cancer therapy for greater than 1 month
- 3.2.21 Known history of HIV.
The effects of J591 are unknown in this population. Furthermore, ketoconazole has many well-described drug-drug interactions which could affect antiviral therapy. If necessary, this population will be studied separately.
- 3.2.22 Currently active other malignancy other than non-melanoma skin cancer.
Patients are considered not to have “currently active” malignancy if they have completed any necessary therapy and are considered by their physician to be at less than 30% risk of relapse.
 - Known history of known myelodysplastic syndrome
- 3.2.23 Adrenal hormone inhibitors (other than ketoconazole) within 4 weeks prior to study enrollment.
- 3.2.24 Finasteride (Propecia® or Proscar®) or dutasteride (Avodart®) within 4 weeks of enrollment.
- 3.2.25 Patients on corticosteroids prior to enrollment must have either discontinued and shown biochemical progression or have biochemical progression on a stable dose

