2.3 Rationale

As stated above, we have validated that J591 can target known sites of disease and have preliminary evidence that there is anti-tumor effect of radiolabeled J591. Since forms of radiotherapy have been validated in the clinically localized as well as salvage setting, “targeted radiotherapy” in the form of radioimmunotherapy is at least theoretically an attractive option with the possibility being a higher yield therapy in the minimal disease (biochemical only) setting [see information on anti-CD20 based radioimmunotherapy above].

The objective of this study is to determine the efficacy of the addition of ^{177}Lu -J591 to ketoconazole in men with progressive biochemical (PSA) prostate cancer despite medical or surgical castration. All subjects will receive ketoconazole (400 mg p.o. TID) plus replacement doses of hydrocortisone (20 mg am, 10 mg pm). Subjects will be randomized to receive a single dose of 70 mCi/m² ^{177}Lu -J591 or trace-labeled ^{111}In -J591 (i.e. placebo). Subjects will be followed for response, disease progression, safety and toxicity. The treatment phase will last until progression of disease or toxicity necessitating discontinuation of therapy. Subjects will be followed until the primary endpoint, which is the development of radiographically apparent metastatic disease.

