4.2 Central Patient Registration

Patients will be centrally registered with the Weill Cornell Medical College (WCMC), Division of Hematology and Medical Oncology Clinical Research Office. To register a patient, upload the following documents into a pdf file(s) and email to [contact] (note that this email address will not accept emails larger than 4.5 MB in size, so large size files may need to be split). If scan/email is not readily available, fax to the Clinical Research Office at [contact]. Fax should be followed by phone call or email to ensure receipt.

- WCMC Patient Enrollment Form
- First and last page of the fully executed informed consent form, plus additional pages if checkboxes for correlative studies are required.
- Fully executed HIPAA research authorization form (if separate from the consent document)
- Eligibility checklist signed and dated by investigator and research nurse
- Source documents verifying eligibility including
 - i. Pathology report confirming diagnosis
 - ii. Laboratory reports confirming PSA progression
 - iii. Radiology reports, bone scan, CT/MRI scan of abdomen/pelvis and Chest x-ray or CT scan
 - iv. Laboratory reports confirming all required eligibility criteria have been met
 - v. On-study visit note documenting PS and consenting process
- Documentation of any eligibility waivers granted

Central registration information is reviewed and entered into the HemOnc centralized research database. These documents should be emailed (or faxed if email is not feasible) Monday to Friday from 9:00 AM to 4:45 PM EST. Patients will be assigned a sequence number for the protocol. The registering institution will then be faxed a copy of the sequence number as confirmation of a completed registration.

Registration of patients cannot occur until the Coordinating Center has received proper documentation from the registering institution of IRB approval, including a copy of the current approval letter, stamped consent and signed FDA-1572 form. These documents may be emailed to [contact] or faxed to the Coordinating Center at [contact].

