5.1.4 Castration

All subjects who have not been surgically castrated will continue to receive LHRH agonist/antagonists to maintain chemically castrated state (goal testosterone < 50) as part of standard care. Examples of acceptable medications include leuprolide and goserelin.

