10.1 STUDY PROCEDURES: Schedule of Events

The assessments to be performed during the study are outlined below by study period, visit and day. Study assessments through Visit 9 (Day 85) will be completed within ± 3 days of the specified day for the visit, except where noted. Visits after Day 169 will be performed within ± 7 days of the scheduled visit.

Screening Period (Visit 1, Days -28 to -1) – All subjects

The procedures outlined for Visit 1 must be completed prior to the patient receiving study drug. The following procedures will be conducted at Visit 1:

- Informed Consent
- Medical History
- Concurrent medications
- Complete Physical Exam
- Vital Signs
- Demographics
- Previous therapy
 - Surgical report will include date and type of surgery +/- lymphadenectomy
 - Radiotherapy report will include modality of therapy with prescribed dose and field and dates of therapy
 - Previous hormonal therapy – drugs, doses, dates of therapy
 - Continuous vs intermittent therapy
- ECOG Performance Status
- Height, Weight
- CBC with differential and platelet count.
- PT or INR, PTT
- Electrolytes, BUN, Creatinine
- Total protein, albumin, calcium, total bilirubin, AST, ALT, LDH
- PSA
- PSA DT Calculation

- Alkaline phosphatase
- Testosterone
- Human anti-J591 antibody sample (may also be drawn C1D1 prior to initiation of study drugs)
- Urinalysis
- Archival Tissue (section 9.1.4) - Paraffin-embedded tumor blocks or 5 unstained slides with representative tumor tissue
- EKG, up to 1 month prior to treatment
- CT or MRI (abdomen-pelvis), up to 4 weeks prior to enrollment
- Bone scan, up to 4 weeks prior to enrollment
 - Any confirmatory tests to assess equivocal results of bone scan should also be completed within 4 weeks of enrollment
 - CXR, up to 4 weeks prior to enrollment (if CT chest has been performed within 4 weeks of enrollment, this procedure is waived)

Evaluations and procedures at Visit 2 (C1D1) – All subjects

Following screening procedures, eligible patients will be dosed with ketoconazole and hydrocortisone. See Section 5.1 for details on the dose and administration.

The following assessments are to be collected prior to drug administration unless otherwise noted:

- Interval medical history
- Targeted Physical Examination with vital signs
- ECOG PS
- CBC with differential and platelet count*
- Electrolytes, BUN, Creatinine*
- PSA*
- Adrenal hormone levels
- Plasma markers
- CTC's
- Adverse Events

- Concomitant medications

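### The testosterone limit in criterion 3.1.6 is written in ng/ml, 100 times the same number in ng/dL, so the only laboratory check of castration at entry has no effect as written

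*Combined protocol and SAP*

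**What the plan says.** Section 3.1 lists the laboratory test of castration as criterion 3.1.6: "Serum testosterone \leq 50 ng/ml". The only other numerical testosterone target is in section 5.1.4, where treatment is meant to "maintain chemically castrated state (goal testosterone < 50) as part of standard care". That passage gives no unit, and it uses a strict inequality where 3.1.6 allows equality.

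Castration also appears without a number. Criterion 3.1.2 requires "Biochemical progression (rising PSA) after medical or surgical castration". Section 5.1.4 adds that "All subjects who have not been surgically castrated will continue to receive LHRH agonist/antagonists". Section 2.3 describes the target population as "men with progressive biochemical (PSA) prostate cancer despite medical or surgical castration".

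Section 4.2 has central registration collect a signed eligibility checklist and "Laboratory reports confirming all required eligibility criteria have been met". The study calendar and section 10.1 schedule testosterone at screening, at PSA progression and at end of study.

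**The concern.** The trial is about castrate-resistant disease, so entry depends on showing that PSA is rising while testosterone is suppressed. Criterion 3.1.2 covers the treatment history and the PSA course but sets no testosterone level. Criterion 3.1.6 is where a level is set, and its unit puts the limit far above what a castration test would need.

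The man at issue has been castrated medically, but his suppression is incomplete or has lapsed. His PSA may rise for that reason and still satisfy the PSA rules in 3.1.2 and 3.1.3. He would not belong to the population in section 2.3, and 3.1.6 as written would not catch him. Because testosterone is next scheduled only at PSA progression, the error might not come to light early.

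**Working it through.** **Nothing to reproduce.** The limit is a fixed cut-off with no derivation in the plan. The check is a unit conversion and a comparison.

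**Step 1: convert the limit.** The input is 50 ng/ml, from 3.1.6.
- 50 ng/mL × 100 mL/dL = 5,000 ng/dL.
- The same number in ng/dL would be 50 ÷ 100 = 0.5 ng/mL.
- Ratio: 5,000 ÷ 50 = 100.

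**Step 2: compare with non-castrate levels.** The documents give no range, so three are assumed.

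| Assumed non-castrate range (ng/dL) | Written limit ÷ upper end | Whole range passes 5,000? | Any of the range passes 50? |
|---|---|---|---|
| 200–800 | 5,000 ÷ 800 = 6.25 | yes | no |
| 300–1,000 | 5,000 ÷ 1,000 = 5.0 | yes | no |
| 250–1,200 | 5,000 ÷ 1,200 = 4.17 | yes | no |

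On each assumption the written limit passes every non-castrate man, and a limit of 50 ng/dL would fail every one. The result does not depend on which range is chosen.

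**Step 3: look for a correction elsewhere.** Section 5.1.4 has no unit, and no section gives testosterone in ng/dL. Neighbouring blood limits are per decilitre (hemoglobin in 3.2.8, creatinine in 3.2.10), while PSA in 3.1.2 is in ng/mL. That pattern suggests a unit slip, but the documents do not say so.

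**Step 4: look for another safeguard.**
- 3.1.2 requires that castration came before the PSA rise. It names no level.
- 5.1.4 governs care during the study. Its wording presupposes current therapy in men without orchiectomy, but it is not an entry test.
- 4.2 checks laboratory reports against the criteria, so for testosterone it would check against the limit in 3.1.6.

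**Step 5: effect on the design figures.** Section 13.1 compares 80% with 50% in about 34 and 17 men at one-sided alpha 10%. With pooled proportion (34 × 0.80 + 17 × 0.50) ÷ 51 = 0.70:
- null SE = √[0.70 × 0.30 × (1/34 + 1/17)] = 0.136
- alternative SE = √[0.80 × 0.20/34 + 0.50 × 0.50/17] = 0.139
- power = Φ[(0.30 − 1.2816 × 0.136) ÷ 0.139] ≈ 0.82

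This agrees with the stated power of at least 80%. Testosterone does not enter the calculation.

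**The case against.** The strongest reply is that inclusion criteria apply jointly. A loose 3.1.6 does not make a man eligible by itself: 3.1.2 still demands progression after castration, 5.1.4 assumes that suppression continues, and an investigator signs a checklist that is reviewed centrally. Most sites may simply read ng/dL. The protocol has another apparent slip of this kind, a PSA rise in mg/mL in 11.2.3.3, where PSA is otherwise in ng/mL. Much of this stands. It limits the consequence but does not supply the missing laboratory threshold.

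A reader might infer more than the documents support:

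- **That non-castrate men in general can enter.** A never-castrated man fails 3.1.2. The gap concerns inadequate or lapsed suppression.
- **That sites must accept any man who passes 3.1.6.** Passing one criterion does not oblige a site to enrol anyone.
- **That men in an off-treatment interval are expected.** The screening item "Continuous vs intermittent therapy" belongs to the record of previous hormonal therapy. It does not say that such men qualify.
- **That each affected man shifts an arm's result by about 6 or 3 percentage points.** Those figures are 1/17 and 1/34. They are the weight of any one patient, and they matter only if his outcome would have differed. Allocation is randomized and blinded, so no bias between the arms is shown.
- **That the 50% control rate depends on this cut-off.** The protocol summary ties the rate to the entry criteria, but section 13.1 attributes it to a cited study. Nothing links it to testosterone.

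**Conclusion.** The point holds in a limited form. The limit in 3.1.6 is 100 times the same number in ng/dL and, read literally, excludes no one. That last statement rests on an assumed upper end of 800 to 1,200 ng/dL for non-castrate men, against which the limit is about 4 to 6 times too high to discriminate. The sole laboratory test at entry of adequate suppression therefore does not work as written, and no other section repairs it. How many men are affected, if any, is unknown. The consequence is uncertainty about whether every enrolled man fits the stated population, and possibly different practice across the 10 to 16 planned sites. It is not a fault in power, alpha or sample size. That ng/dL was intended is the likely reading, but it is for the sponsor to confirm.

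**What to change.** The sponsor should state the intended unit and correct 3.1.6. Sections 3.1.6 and 5.1.4 should then be reconciled on the unit and on whether equality is allowed; since 5.1.4 is an on-treatment goal, its content is the sponsor's decision. The eligibility checklist is not among the documents, so it should be checked for agreement with the corrected criterion.

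For men already enrolled, compare the screening testosterone with the corrected limit before analysis and report how many exceed it. Under section 13.1 the intent-to-treat analysis keeps all randomized men. The study-drug subset requires that eligibility was met, so the plan should say in advance which limit defines eligibility for men enrolled under the present text.

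The cost is small: a one-word amendment to 3.1.6, a matching clarification in 5.1.4, and a review of values already collected at screening. A few inadequately suppressed men would fail screening, which may slow accrual slightly.
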